1.1.2 Secondary hypotheses

- 1.1.2.1 Subjects randomized to the ALERT specialist arm will have higher ART uptake compared to subjects in the SOC arm.
- 1.1.2.2 Use of detailed assessments at study entry will allow for the identification of covariates associated with poor retention and initiation of ART.
- 1.1.2.3 Use of an ALERT specialist and a structured retention module intervention will modify the impact of covariates on retention and initiation of ART.

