1.3 Secondary objectives

- 1.3.1 To evaluate the effect of an ALERT worker on the time to initiation of ART per DHHS guidelines.
- 1.3.2 To assess factors predictive of loss to care, such as demographic, socioeconomic, and psychosocial factors, risk behavior, substance use and psychiatric illness.
- 1.3.3 To assess if the ALERT intervention mitigates the impact of psychosocial barriers on retention in care and initiation of ART.
- 1.3.4 To compare in the intervention vs. SOC arm (assessed at 12 month intervals):
 - 1.3.4.1 Baseline and annual scores on standardized assessments of HIV literacy, disclosure and social support, perception of stigma, barriers to care, ART adherence and Intention to Adhere, Beck Depression Index, substance use evaluations, HIV high-risk

		transmission behaviors, and measures of self-efficacy
	1.3.4.2	Number of visits per year with HIV prescribing provider per year
	1.3.4.3	HIV RNA < 50 and 200 copies/mL at 12 months and every 12 months thereafter
	1.3.4.4	CD4 cell counts and changes from baseline in CD4 at 12 months and every 12 months thereafter
	1.3.4.5	Time to AIDS diagnosis or death
1.3.5		e reasons identified in the refusal survey why patients who are study decline study participation

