9.4 Sample Size and Accrual

9.4.1 Power and Sample Size Justification

The primary outcome for this study is to compare the time to LTFU. A secondary outcome is time to initiation of ART. Sample size calculations were based on a two-sided, two-sample log-rank test to compare the differences in time to the-primary endpoint proportions between the intervention arm and the standard of care arm.

Since attrition is a component of the composite endpoint, attrition rates are not used as an adjustment in the power calculations. Assuming 150 subjects per group in each of the two

Table 5: Power based on a two-sided, log-rank test with alpha=0.05 and N=150 per arm (total N = 300)							
Composite	Composite rate	Corresponding	Statistical				
rate without	without	Hazard Ratio	Power (%)				
Endpoint in	Endpoint in	(HR)					
SOC (%)	Intervention						
	(%)						
65	80	1.93	82				
65	85	2.65	97				
70	85	2.19	87				
75	87.5	2.15	78				
75	90	2.73	92				
80	92.5	2.86	87				
80	95	4.35	97				

groups (for a total of 300 subjects), we have 87% power to detect a difference of 15%, assuming a time without a composite endpoint rate of 70% in SOC arm and that the intervention arm will increase the time without an endpoint (to a rate to 85%). This corresponds to a hazard ratio of 2:19. Table 5 shows other possible standard of care rates between arms (and hazard ratios), and corresponding statistical power. The calculations assume that the hazard rates are proportional.

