9.6.2 Analysis of Primary Outcome

A survival analysis of "time to LTFU" will be conducted. LTFU is defined as no visit with a prescribing HIV provider in the last 180 days. Time-to-LTFU will be calculated as total days between the first visit and the date when the participant reaches the definition of LTFU.

For example, a subject has his first visit on Jan 1, 2013, and another visit on Mar 1, 2013. If the subject does not have any visits thereafter, or does not have any visits until >180 days later, the subject will be counted as reaching the primary endpoint of LTFU. In this case, the subject would be LTFU if no visit occurred before Aug 27, 2013, (which is 180 days past Mar 1st). The "time-to-LTFU" will be the time period between Jan 1, 2013 and Aug 27, 2013.

At the end of the study, patients who have not reached the primary endpoint will be censored at the time of their last quarterly data extraction.

Patients who meet the primary endpoint and are found to be incarcerated will be removed from the study and censored effective at the time of their incarceration. Those who are incarcerated but return to care upon release, prior to reaching a primary endpoint, will be allowed to remain in study. Patients who change care provider to an external health facility (such as a different clinic system or a nursing facility) will be assessed for their current engagement in care; those who have completed a clinic visit with a prescribing clinician within the 180 days will be considered engaged in

care, and will not be considered LTFU. If possible, these patients will continue to come in for annual study visits.

The null hypothesis is that the median time-to-LTFU estimated using the Kaplan-Meier method will be identical in both groups. The log-rank test will be used to test the null hypothesis against the alternate hypothesis that the median time-to-LTFU is not the same between the groups.

In addition, to assess the factors associated with time-to-LTFU, Cox regression models will be performed on two subgroups, looking at each arm separately. The model will have time to LTFU as the outcome, baseline variables such as demographic, socioeconomic, psychosocial factors, risk behavior, substance use and psychiatric illness as predictors.

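### Predictors of loss to follow-up and of ART initiation are modelled only within each arm; the text gives neither a pooled model for the overall question nor an interaction test for the effect-modification question

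*Combined protocol and SAP*

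**What the plan says.** Objective 1.3.2 is "To assess factors predictive of loss to care, such as demographic, socioeconomic, and psychosocial factors, risk behavior, substance use and psychiatric illness". Hypothesis 1.1.2.2 expects that the entry assessments "will allow for the identification of covariates associated with poor retention and initiation of ART". Neither is worded by arm.

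A separate pair of aims concerns effect modification. Objective 1.3.3 is "To assess if the ALERT intervention mitigates the impact of psychosocial barriers on retention in care and initiation of ART", and hypothesis 1.1.2.3 makes the matching prediction.

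The only predictor analysis described for LTFU is in section 9.6.2: "Cox regression models will be performed on two subgroups, looking at each arm separately". It uses "baseline variables such as demographic, socioeconomic, psychosocial factors, risk behavior, substance use and psychiatric illness as predictors". That is six domains in an open-ended list, with no number of terms and no selection rule. Section 9.6.3 repeats the approach for time to ART initiation. Section 9.6.1 tests secondary analyses at 0.05 without multiplicity adjustment.

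**The concern.** Two questions are run together. Which baseline factors predict loss to care is a main-effect question, and all randomised participants carry information on it. Whether ALERT changes the effect of a factor is an interaction question. Two separate fits serve neither well. Each main effect is estimated from part of the events, and the smaller part is in the arm where the intervention is expected to prevent events. Nothing formally compares the coefficients between arms.

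The practical risk is discordance. A factor that acts identically in both arms can easily be significant in one model and not in the other. A reader may then conclude that ALERT removed a barrier, which is the claim in objective 1.3.3, when only the event counts differ.

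**Working it through.** **Inputs from the documents.** 150 per arm and two-sided alpha 0.05 (Table 5, section 9.4.1). The planning case is 70% endpoint-free in SOC and 85% in ALERT: "we have 87% power to detect a difference of 15%, assuming a time without a composite endpoint rate of 70% in SOC arm".

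**Inputs assumed.** The documents give no hazard ratio (HR) or prevalence for any risk factor. I take HR 2.0 and 50% prevalence as the reference and vary both.

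**Step 1: reproduce the plan's figure.** HR = ln(0.70)/ln(0.85) = 2.195. Events D = 150 × 0.30 + 150 × 0.15 = 67.5. Freedman power = Φ(√67.5 × 1.195/3.195 − 1.96) = Φ(1.11) = 86.7%, against 87% stated. All seven rows of Table 5 reproduce within 0.5 point, so event counts derived this way match the plan's own basis.

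**Step 2: events per model**, as 150 × (1 − endpoint-free proportion).

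| | ALERT | SOC | Pooled |
|---|---|---|---|
| Planning case 70/85 | 22.5 | 45 | 67.5 |
| Range over Table 5 | 7.5–30 | 30–52.5 | 37.5–82.5 |

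With only one term per named domain (six terms), the planning case gives 22.5/6 = 3.75 events per term in ALERT and 45/6 = 7.5 in SOC.

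**Step 3: power for a factor with the same effect in both arms.** At 50% prevalence SE(log HR) = 2/√events, and power = Φ(ln HR/SE − 1.96).

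At HR 2.0, ln 2 = 0.693:
- ALERT: SE 0.422, power 38%
- SOC: SE 0.298, power 64%
- Pooled: SE 0.243, power 81%

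**Step 4: sensitivity to the assumed HR** (planning case, 50% prevalence; loss is relative to pooled).

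| HR | ALERT | SOC | Pooled | Loss, ALERT | Loss, SOC |
|---|---|---|---|---|---|
| 1.5 | 16% | 27% | 38% | 59% | 29% |
| 2.0 | 38% | 64% | 81% | 54% | 21% |
| 2.5 | 58% | 87% | 96% | 39% | 10% |
| 3.0 | 74% | 96% | 99% | 26% | 4% |

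At 20% prevalence the ALERT loss is 58% at HR 2, 52% at HR 2.5 and 42% at HR 3. Across Table 5 rows at HR 2 and 50% prevalence it runs from 46% (65/80) to 72% (80/95).

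**Step 5: sensitivity to follow-up.** Table 5 states no time horizon, and follow-up runs on until the last enrolled participant reaches 48 weeks. Suppose its rates are 48-week rates with constant hazard (an assumption); then events = 150 × (1 − S^k) for average follow-up of k times 48 weeks.
- k = 1.5: 32 ALERT and 62 SOC events. Power at HR 2 is 51%, 78% and 92% pooled; ALERT loss 45%.
- k = 2: 42 and 76.5 events. Power is 61%, 86% and 96%; ALERT loss 37%.

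**Step 6: discordance and error** (HR 2.0 in both arms, planning case, arms independent).
- Both models significant: 0.376 × 0.642 = 24%.
- Exactly one significant: 0.376 × 0.358 + 0.624 × 0.642 = 54%.
- At least one significant: 1 − 0.624 × 0.358 = 78%, against 81% pooled.
- Null error if a factor counts when either model is significant: 1 − 0.95² = 9.75%.

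**The case against.** The best defence is that arm-specific models are meant for objective 1.3.3 and hypothesis 1.1.2.3. That is plausible, but section 9.6.2 gives their purpose as finding factors associated with time to LTFU, which is objective 1.3.2. Separate fits would not test effect modification in any case.

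Several stronger readings are tempting and are not supported:
- A reader might infer that splitting loses over half the power in general. In the planning case at 50% prevalence this holds only for the ALERT model and only up to an HR of about 2. The SOC loss is 4% to 29% over HR 1.5 to 3.
- A reader might take 7.5 events as the expected ALERT count. It is the extreme row of Table 5; the planning case gives 22.5.
- A reader might count the instruments in objective 1.3.4.1 and infer a model of about a dozen terms. Those instruments are listed for comparing the arms, and the plan fixes no number of terms.
- A reader might infer that the trial would find few predictors. At HR 2.0 at least one model flags the factor 78% of the time. The harm is mainly conflicting results and a raised error rate.

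Two further points stand. Section 9.0 says that a SAP gives the details and takes precedence. No separate SAP text is available here, and if it specifies a pooled model with interactions the point is already met. Table 5 concerns LTFU only, so none of these event counts applies to ART initiation.

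**Conclusion.** The concern holds as a mismatch between stated aims and stated method. The text answers an overall predictor question with arm-specific models alone, and it provides no test for the effect-modification question.

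The size depends on an HR and a prevalence that the documents do not give, and on the Table 5 event rates. At HR 2.0 and 50% prevalence in the planning case, ALERT power is less than half the pooled power. The gap narrows for stronger factors and for longer follow-up. The most consequential figure is the 54% chance that the two models disagree on a factor that acts the same in both arms.

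This is a secondary analysis, and the correction is worth making because it is cheap. For ART initiation only the structural argument carries over.

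**What to change.** **Overall predictors (1.3.2, 1.1.2.2).** Pre-specify one Cox model in all randomised participants, stratified by or adjusted for arm. Enter clinic site and new/returning status as covariates; stratifying the model on them would prevent their estimation as predictors. Name a short predictor list in advance, sized to the expected events.

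**Effect modification (1.3.3, 1.1.2.3).** Add a small pre-named set of arm-by-covariate interaction terms to the pooled model, and base any statement about mitigation on those terms. Keep the within-arm models as descriptive tables.

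**ART initiation (9.6.3).** Use the same structure, with the predictor list sized to the ART-initiation events expected, not to the LTFU figures above.

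**Cost.** SAP wording and one added model per outcome; no new data. If effects differ by arm, the pooled main effect is an average, which the within-arm tables would help to show. The interaction terms will have low power: at 50% prevalence in the planning case the SE of a log ratio of hazard ratios is √(4/22.5 + 4/45) = 0.516, so a twofold ratio is detected with power Φ(0.693/0.516 − 1.96), about 27%. They should therefore be reported as estimates with confidence intervals.

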9.6.3 Analysis of Secondary Outcomes

Main Secondary Outcome: The CCTG 594 secondary outcome is time to initiation of ART. A survival analysis of time to initiation of ART will be conducted. Time to initiation of ART will be calculated as total days between the first visit to the ART start date. For those participants who do not start ART, the time to initiation of ART will be censored to the participant's last visit date.

The NULL hypothesis is that the median time to initiation of ART estimated using the Kaplan-Meier method will be identical in both groups. The log-rank test will be used to test the null hypothesis against the alternate hypothesis that the median time to initiation of ART is not the same between the groups.

In addition, to assess the factors associated with time to initiation of ART, Cox regression models will be performed on two subgroups, looking at each arm separately. The model will have time to initiation of ART as the outcome, baseline variables such as demographic, socioeconomic, psychosocial factors, risk behavior, substance use and psychiatric illness as predictors.

9.6.4 Other Secondary Analyses

Descriptive analyses will be conducted for all the secondary analyses including comparisons between randomized groups on the following measures:

- Baseline and follow-up scores on HIV and health literacy assessments, disclosure rates, adherence, and measures of selfefficacy
- Number of primary care visits per year
- HIV RNA < 50 and <200 copies/mL at years 1 and 2
- CD4 cell counts and changes from baseline in CD4 at years 1 through 2
- Scores on Beck Depression Index
- Substance use
- HIV high-risk transmission behaviors
- Time to AIDS diagnosis or death
- Reasons eligible patients decline study participation

For patients who meet the primary endpoint (LTFU) but subsequently return to care, secondary analyses will measure the proportion returning in the intervention vs. SOC arm and the time between their last and return visit with a prescribing provider.

Fisher's exact test will be used for categorical variables; T-test (or Wilcoxon Rank Sum test, if parametric assumptions fail) will be used for continuous variables.

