4.0 SELECTION AND ENROLLMENT OF SUBJECTS

4.1 Inclusion Criteria

- 4.1.1 HIV-1 infection, as documented by any licensed screening antibody test, such as ELISA, and confirmed by a second antibody test, such as Western blot, or detectable plasma HIV-1 RNA at any time prior to study entry. If an ELISA or Western blot is not available, HIV infection may be documented by two HIV RNA values ≥2000 copies/mL, drawn at least 24 hours apart. The RNA assays must have been run at a CLIA-approved laboratory or equivalent.
 4.1.2 18 years of age or older.
- 4.1.3 Able to give written informed consent.
- 4.1.4 New patient to the clinic (defined as someone who has never engaged in HIV care) or a patient returning to care (defined as a patient previously seen at least once by a prescribing HIV provider who has not seen a prescribing HIV provider in the last 180 days and is not on a stable ARV regimen).
- 4.1.5 English or Spanish Speaking.
- 4.1.6 Registered to receive HIV primary care services at one of the identified CCTG-affiliated clinic, i.e. the Owen Clinic at UC San Diego Health System, Harbor-UCLA Medical Center clinic or Rand Schrader clinic at USC.

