6.2.2 Entry Evaluations and Randomization

Entry must occur within 60 days of the patient's first primary care visit (for patients new to care) or their first primary care re-entry visit (for patients returning to care). At study entry, baseline surveys will be collected utilizing the web-based, computer-assisted system on the study specific portal (to view baseline survey, see Attachment 5, *iPad Assessments for CCTG 594*). The portal will allow private completion of questionnaires without concern that clinic or study personnel can view the subject's responses in order to encourage candor.

Subjects will be randomized (1:1) to SOC or ALERT Intervention study arm. Randomization will be stratified by clinic site and whether the subject is newly diagnosed or returning to care. A total of 300 subjects

(150 per arm) will be randomized and followed for a minimum of 48 weeks. SOC will be the clinic standard.

Samples of plasma will be stored for future assays.

6.2.3 On-Study Evaluations

Study specific follow-up visits for each subject will be kept to a minimum in order not to bias the outcome of lost to follow up. Our experience suggests that involvement in a research protocol, with the extra effort the coordinators exert to ensure study follow-up, could easily impact on attendance to clinical care. Thus, for SOC patients, study specific visits will occur yearly preferably in conjunction with a regularly scheduled clinic visits (see below, *yearly study visits*).

In the ALERT intervention arm, the ALERT specialist will conduct 5 monthly educational retention modules (in person or by phone). The ALERT specialist will also continuously monitor and track all health care visits to ensure healthcare continuity, and will intervene using described tools/methods when the subject does not have a visit within a predetermined interval (see Attachment 4, *Manual of Operating Procedures*, for ALERT Specialist job description, methods, and Retention Modules).

6.2.4 Data Abstraction

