9.6 Analyses

9.6.1 Statistical Analysis Plan

In general, analyses will incorporate the intent-to-treat principle, namely, all randomized participants will be included in the analysis. The primary analysis compares the ALERT Intervention to the SOC arm. For all secondary analyses of interest, no adjustments for multiple comparisons will be made, and a p-value of 0.05 will be considered statistically significant. Demographic and baseline measurement variables will be summarized via standard descriptive statistics.

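### Time to ART initiation has no rule for ART started before randomisation and does not define the event for ART-experienced patients

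*Combined protocol and SAP*

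**What the plan says.** Objective 1.3.1 reads: "To evaluate the effect of an ALERT worker on the time to initiation of ART per DHHS guidelines". Section 9.6.3 makes this the main secondary outcome and defines it: "Time to initiation of ART will be calculated as total days between the first visit to the ART start date". Participants without an event are handled thus: "For those participants who do not start ART, the time to initiation of ART will be censored to the participant's last visit date". The arms are compared by log-rank test, and Cox models are then fitted within each arm on the same times.

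Section 9.6.1 sets the analysis population: "all randomized participants will be included in the analysis". Section 9.6.3 makes no exception to it.

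On timing, section 6.2.2 states: "Entry must occur within 60 days of the patient's first primary care visit". The same limit applies to the re-entry visit of a returning patient, and section 4.2.5 repeats it as an exclusion.

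On ART at entry, section 4.1.4 restricts only returning patients, described as someone "who has not seen a prescribing HIV provider in the last 180 days and is not on a stable ARV regimen". The word *stable* is not defined. A new patient is one who has never engaged in HIV care, with no condition on ART prescribed between the first visit and entry.

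**The concern.** The objective is about what ALERT does to ART uptake. Only participants not taking ART when the arm is assigned can show that effect. Section 9.6.3 does not limit the analysis to them, does not start the clock at randomisation, and does not say what counts as initiation in someone who has taken ART before.

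At stake is the estimate for the main secondary endpoint. Starts before randomisation carry no information about ALERT, and counting them mixes a ratio of 1 into the result. The within-arm Cox models would inherit the same faulty times.

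**Working it through.** **1. Can ART start before randomisation?** Yes. Up to 60 days may pass between the care visit and entry (sections 4.2.5 and 6.2.2). New patients have no ART restriction. A returning patient who restarts at the return visit may not yet be on a stable regimen. Sections 6.3.2 and 6.3.3 collect ARV history and a 30-day medication history with start dates, so the protocol itself allows for past or recent ART use.

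**2. What is the first visit?** Section 9.6.3 does not say. For the primary outcome the document uses three origins: study entry (Schema), baseline visit (section 9.2) and first visit (section 9.6.2).

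- Care-visit reading: an ART start before randomisation is an ordinary early event, credited to an arm not yet assigned.
- Baseline-visit reading: the same start gives a negative time (zero if it falls on that day), and no rule covers it.

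**3. What is the event in an ART-experienced returning patient?** If it is the first-ever start, the time is negative under either reading. If it is a restart, the time can be valid, but the text does not say that restarts count.

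**4. The plan's own power figure.** None exists for time to ART. Table 5 (section 9.4.1) concerns LTFU and reproduces. For 70% v 85% event-free, HR = ln 0.70 / ln 0.85 = 2.19. Events = 150 × (0.30 + 0.15) = 67.5. Freedman power = Φ(√67.5 × 1.19/3.19 − 1.96) = 86.7%, against the stated 87%. This point does not touch it.

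**5. Illustrative size, care-visit reading only.** Taken from the documents: 300 patients, 1:1, two-sided 5%, at least 48 weeks (336 days) of follow-up. Assumed: entry uniform over 0–60 days, exponential time to ART with median m in the SOC arm, the SOC hazard in both arms before randomisation, and a true ratio of 1.5 afterwards.

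Share starting before randomisation, with λ = ln 2 / m:

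f = 1 − (1 − e^(−60λ)) / (60λ)

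For m = 30: 60λ = 1.386, so f = 1 − 0.75/1.386 = 0.459. For m = 60: f = 1 − 0.50/0.693 = 0.279. For m = 120: f = 1 − 0.293/0.347 = 0.155. For m = 180: f = 1 − 0.206/0.231 = 0.107.

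The apparent ratio is roughly 1.5^(1−f), giving 1.25, 1.34, 1.41 and 1.44. Strictly, f should be the share of events, which is slightly larger when not everyone starts (13% rather than 11% at m = 180). Simulation gives:

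| SOC median to ART (days) | Start before randomisation | HR, care-visit clock, all counted | Power | HR, from randomisation, not on ART | Power |
|---|---|---|---|---|---|
| 30 | 46% | 1.24 | 44% | about 1.5 | 72% |
| 60 | 28% | 1.33 | 68% | about 1.5 | 83% |
| 120 | 15% | 1.40 | 79% | about 1.5 | 86% |
| 180 | 11% | 1.43 | 79% | about 1.5 | 84% |

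A separately coded run (1,500 trials per scenario; medians 30, 60, 90 and 180) gave 1.24, 1.33, 1.38 and 1.42, with power 44%, 69%, 77% and 78%, against 71%, 84%, 87% and 82% corrected. With a true ratio of 1.3 it gave 1.15, 1.21, 1.23 and 1.26, with power 23%, 37%, 42% and 42%, against 39%, 48%, 51% and 47%.

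**The case against.** The strongest reply has four parts.

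*ART-experienced patients are a legitimate target.* A reader might infer that they all contribute events beyond ALERT's reach and should be removed. The documents do not support that. Returning patients are enrolled by design (sections 2.2.1 and 4.1.4), and ALERT can influence a restart after randomisation. For them the defect is an undefined event.

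*The returning stratum is not left without an outcome.* A reader might infer that the endpoint has no valid value there. A returning patient needs only one earlier visit with a prescriber, so some may be ART-naive and have an ordinary value. For the others, the negative time arises only if a historical date is used. No section instructs that, and section 6.3.5 records on-study starts and modifications. The text is ambiguous rather than unusable for this stratum.

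*The size is assumed.* This stands in full. The 60 days are a ceiling, not a distribution, and the hazard ratio, medians and exponential form are not in the documents. The figures also need the care-visit reading. Under the baseline-visit reading, dropping the invalid records would give much the same set as the fix.

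*Section 9.0 defers to a separate SAP, which takes precedence.* No such text is in the supplied document. It may hold a rule, and this limits confidence.

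None of this supplies the missing rule. Following section 9.6.3 literally gives a diluted estimate under one reading and impossible times under the other.

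**Conclusion.** The definition is wrong as written, for a secondary endpoint; confidence is moderate. The certain part is structural: the origin and event are undefined, and nothing covers ART begun before randomisation. The direction under the care-visit reading is toward no effect. Pre-randomisation starts should balance between arms on average, so this is not a source of false positive findings.

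The size is uncertain. Under the stated assumptions, power falls by 28 points (72% to 44%) if the median time to ART is 30 days, but by only 5 points (84% to 79%) if it is 180 days. These figures do not model ART-experienced patients and should not be read as what the trial will show. The primary endpoint and Table 5 are unaffected.

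**What to change.** First check whether a separate SAP already holds a rule. If not, amend section 9.6.3 before analysis:

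- Time origin: randomisation.
- Analysis set: participants not taking ART at randomisation. Use the ARV and 30-day medication history. Because screening may precede entry by up to 30 days (Table 1, footnote 1), confirm status against the ART dates in the chart abstraction.
- Event: the first ART start or restart dated after randomisation. State in advance how a start on the day of randomisation is treated.
- Reporting: the number already taking ART at randomisation, by arm, and results by the existing new/returning stratum, so that first starts and restarts can be told apart.
- Apply the same definition to the within-arm Cox models.

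The cost is wording only, since the data are already collected (sections 6.3.2, 6.3.3 and 6.3.5). The downside is a smaller set for this endpoint: in the illustration, about 162 of 300 remain at a 30-day median (300 × 0.541) and about 268 at 180 days (300 × 0.893). Because the set is defined by status before randomisation, the randomised comparison is kept. Excluding all ART-experienced patients is unnecessary and would lose part of the target population.
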